2.0 OBJECTIVES AND SCIENTIFIC AIMS

Primary Objective:

- To determine Overall Response Rate [ORR = Complete Response (CR) + Partial Response (PR)] by RECIST v 1.1 ≤ 24 weeks from the start of treatment

Secondary Objectives:

- To determine Progression Free Survival (PFS) rate at 24 weeks
- To determine Clinical Benefit Rate (CBR) by 24 weeks
- To determine PFS and Overall Survival (OS)
- To determine Duration of Response (DOR)
- To determine the rate of Serious Adverse Events (SAE) of ZW25 by Common Terminology Criteria for Adverse Events version 5 (CTCAE v 5.0)

Exploratory Objectives:

1. Anti-drug antibodies (ADA) will be assessed at baseline (baseline ADA can be collected on C1D1 pre dose) and pre-dose at Cycles 2, 4, 6, 8, 12, 18, 24 Day 1. The immunogenicity testing will be performed using validated assays in 3 steps as follows: screening assay (Tier 1), confirmation assay (Tier 2), and titration (Tier 3). Only samples positive in the screening assay will be tested in confirmation and further titrated to determine the titer of ADA.
2. To explore the molecular associations between the *HER2* biomarkers: gene amplification (by Next Generation Sequencing [NGS] and in situ Hybridization [ISH]), protein overexpression by immunohistochemistry (IHC) and mutational status and/or copy # variations of relevant cancer-related genes using MSK-IMPACT platform in all patients with new research biopsies collected under this protocol, and to determine mechanisms of underlying response and resistance. Mandatory pre-treatment and post-treatment (collected upon progression of disease) tumor biopsies will be obtained on all patients for this purpose. Tissue testing will be performed in the Center for Molecular Oncology.
3. To examine ORR in each cohort by different types of molecular alterations, *HER2* amplification (by NGS and ISH separately), mutation and *HER2* overexpression, and assess genomic changes with response for potential predictive signatures.
4. To evaluate the predictive value of changes in circulating tumor DNA variant allele frequency during treatment for response to ZW25.

Memorial Sloan Kettering Cancer Center
[name]
[name]

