As of 31 October 2018, a total of 67 patients have been enrolled and treated in Parts 1 and 2 of the study (5 mg/kg QW, n=3; 10 mg/kg QW, n=13; 15 mg/kg QW, n=7; and 20 mg/kg Q2W, n=44). Across all dose levels, the median age is 59 years (range, 27–79). More patients are female (74.6%) than male (25.4%), the majority are white (76.1%), and the majority have an Eastern Cooperative Oncology Group (ECOG) performance status of 1 (73.1%). There are no notable differences in demographics or baseline characteristics between dose levels. Most patients have a disease diagnosis of breast cancer (n=39, 58.2%). Additionally, 9 patients (13.4%) have gastric cancer, 4 each (6.0%) have esophageal or colorectal cancer, and 2 (3.0%) have gall bladder cancer. Other disease diagnoses in 1 patient each include adenocarcinoma of the sigmoid colon, cholangiocarcinoma, undifferentiated adnexal carcinoma of the skin, and bladder, cervical, endometrium, fallopian tube, parotid, and rectum cancers. Overall, nearly all the patients have disease with HER2-high expression (IHC 3+ or IHC 2+/FISH+) by local or central review (85.1%). Disease characteristics are generally similar between dose levels. Most patients have received prior HER2-targeted therapies, with 59 (88.1%) receiving trastuzumab (HERCEPTIN®), 36 (53.7%) receiving pertuzumab (PERJETA®), 39 (58.2%) receiving ado-trastuzumab emtansine (KADCYLA®), 18 (26.9%) receiving lapatinib (TYKERB®), and 1 (1.5%) receiving neratinib (NERLYNX®).

Memorial Sloan Kettering Cancer Center
[name]
[name]

Approximately one-third of the response-evaluable patients treated with single-agent ZW25 in Parts 1 and 2 of the study have achieved an objective response (n=15/48 [31.3%]; all partial responses [PRs]) and approximately two-thirds of patients have experienced disease control (n=32/48 [66.7%]; 15 PRs and 17 stable disease). Regardless of dose level of ZW25, 17 patients (60.7%) with breast cancer have experienced disease control, including 8 with a PR and 9 with stable disease. Six patients (66.7%) with GEA have experienced disease control, 4 with PR and 2 with SD. Nine additional patients (81.8%) with other cancers also have experienced disease control, including 2 PRs and 3 SDs in colorectal cancer (CRC), 2 PRs in gall bladder cancer, 1 PR in cholangiocarcinoma, and 1 SD each in fallopian tube cancer, endometrium cancer, and parotid cancer.

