Lesions with prior local treatment: Lesions situated in a previously irradiated area, or in an area subjected to other locoregional therapy, are usually not considered measurable; however, if they meet the following criteria, they may be considered for study:

- there has been prior documented progression in the lesion by at least 2 sequential CT or MRI scans performed after the completion of radiation, or

- histopathological evidence of progression

Additionally, if such lesions meet the criteria for measurability, they may be considered target lesions.

Imaging Methods:

The same method of assessment and the same technique used to characterize each identified and reported lesion at baseline should be used during each follow-up assessment. Imaging-based evaluation is preferred to evaluation by clinical examination unless the lesion(s) being followed cannot be imaged but are assessable by clinical exam (referring to biopsy-proven visible lesions(s) at the vaginal apex).

Chest X-ray: Lesions that are identified on chest X-ray must be confirmed and followed by CT scan. If there is/are pre-existing chest lesion(s) before the baseline tumor assessment, a chest X-ray is not necessary to assess those lesions. The pre-existing chest lesion(s) must be assessed at baseline and followed by CT scans.

Conventional CT or MRI: This guideline has defined measurability of lesions on CT scan based on the assumption that CT slice thickness is 5 mm or less. If CT scans have slice thickness greater than 5 mm, the minimum size for a measurable lesion is twice the slice thickness. MRI is also acceptable in certain situations (e.g., for body scan) except for lung.

Other methods of assessment, PET-CT, ultrasound and FDG-PET should not be used for response assessment in this study.

Time Point Assessments:

Patients will have tumor measurements performed within 28 days prior to baseline and every 8 weeks through Week 24 and then every 12 weeks after 24 weeks, per RECIST 1.1 guidelines.

At baseline, tumors and lymph nodes are classified and documented as target or non-target per the definitions provided above. It is possible to record multiple non-target lesions involving the same organ as a single item (e.g., 'multiple liver metastases').

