At all post-baseline evaluations, the baseline classification (target, non-target) is to be maintained and lesions are to be documented and described in a consistent fashion over time (e.g., recorded in the same order on source documents and CRFs).

For target lesions, measurements should be taken and recorded in metric notation. All tumor measurements must be recorded in millimeters.

At each assessment, a sum of the diameters (longest for non-nodal lesions, short axis for nodal lesions) for all target lesions will be calculated and reported. The baseline sum of the longest diameters (SLD) will be used as reference to further characterize any objective tumor regression in the measurable dimension of the disease. The lowest SLD (nadir) since, and including, the baseline value will be used as reference for evaluating progression.

After baseline, the actual size of the target lesion should be documented, if possible, even if the lesions become very small. If in the opinion of the radiologist, the lesion has likely disappeared, 0 mm should be recorded. If the lesion is present but too small to measure, an indicator of "too small to measure" will be provided on the CRF (a default value of 5 mm will be imputed during analysis).

Non-target lesions are to be assessed qualitatively (present, resolved, or unequivocal progression) and new lesion, if any, are to be documented separately.

At each evaluation, a time point response is to be determined for target lesions, non-target lesions, new lesions and overall.

Time Point Response Criteria

Target Lesion Time Point Response (TPR)	
Complete Response (CR)	Disappearance of all target lesions. All pathological lymph nodes (whether target or non-target) must have reduction in short axis to < 10 mm.
Partial Response (PR)	At least 30% decrease in the SoD of target lesions, taking as reference the baseline SoD
Progressive Disease (PD)	At least a 20% increase in the SoD of target lesions, taking as reference the smallest (nadir) SoD since and including baseline. In addition to the relative increase of 20%, the SoD must also demonstrate an absolute increase of at least 5 mm.
Stable Disease (SD)	Neither sufficient shrinkage to qualify for PR nor sufficient increase to qualify for PD.
Not Applicable (N/A)	No target lesions identified at baseline

Unable to Evaluate (UE)	One or more target lesions are not imaged and the remainder of the SoD compared with the nadir SoD does not meet the criteria for PD

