Confirmation - The main goal of confirmation of objective response is to avoid overestimating the observed response rate. For patients with an overall response of PR or CR a given time point, changes in tumor measurements must be confirmed by repeat assessments that should be performed no less than 4 weeks after the criteria for response are first met. However, the presence or absence of confirmation is not considered when assigning a time point response.

Best Overall Response - Best overall response, incorporating confirmation requirements, will be derived during statistical analysis from the series of time point responses and need not be considered when assigning response at any time point.

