14.0 BIOSTATISTICS

14.1 Populations for Analyses

All treated population: all treated patients regardless if they completed cycle 1 or the amount of drug received.

Efficacy population: All treated patients except patients without a post baseline assessment of response will be excluded.

Sample Size

This study aims to assess the activity of ZW25 in advanced HER2 overexpressing endometrial cancers and carcinosarcomas as measured by the best overall response rate as determined by RECIST 1.1. Assuming we use a binary endpoint of response, defined as best overall response of CR or PR versus not (best overall response \leq 24 weeks from the start of treatment), a sample size of 25 patients provides 90% power to test the hypothesis that the response rate is promising (defined as 30% or higher) against a non-promising rate of 10% or lower. This calculation is based on historical data from studies with ineffective agents in a similar patient population, which have ORR $<$ 10% and PFS rate at 6 months $<$ 20%,^{7,49-51} and uses a two-stage minimax Simon design, with Type I error=10%. Sixteen patients will be enrolled in the first stage and if 1 response is observed among the 16 the study will end for lack of activity. If \geq 2 responses out of 16 are observed, the study will continue to stage 2, where an additional 9 patients will be enrolled for a total of 25. At the end of the study, if at least 5/25 responses are observed then this will be considered a positive study (i.e. conclude that ORR is $>$ 10%).

Based on historical accrual rates in similar populations, and with the increased prior lines of therapy that will not be allowed for eligibility, we anticipate successful enrollment of 2 patients per month yielding a total accrual time of 18 months. Accrual will continue until 25 evaluable for efficacy response patients are treated (i.e. 25 patients in efficacy population as defined above).

Sensitivity analysis for ORR will include in the calculation of ORR patients who do not have post baseline assessment of response as failures.

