All statistical analyses will be performed using the most recently released version of SAS statistical software, unless otherwise noted. For categorical variables, the number (n) and percent of each category within a parameter will be presented. For continuous variables, the sample size (n), mean, median, and standard deviation, as well as the minimum and maximum values, will be presented. Missing data will not be imputed unless otherwise stated. There will be a detailed description of patient disposition, patient demographics, and baseline characteristics.

We will report the following statistics for the secondary objectives:

- The clinical benefit rate (CBR) of ZW25 therapy, defined as the percentage of patients with complete response (CR) + partial response (PR) + stable disease (SD) ≤24 weeks from the start of treatment will be reported and the 90% confidence interval will be estimated using exact binomial proportions
- Progression free survival (PFS), defined as the duration of time from start of treatment to time of recurrence, progression, or death due to any cause, whichever occurs first will be reported. Patients will be censored at last follow up date. The Kaplan Meier estimate of median PFS will be reported.
- Overall survival is defined as the duration of time from start of treatment to time of death due to any cause. Patients who are alive will be censored at last follow up date. The Kaplan Meier estimate of median OS will be reported.
- The duration of response (DOR) of ZW25 therapy, defined as the time from which measurement criteria are met for CR or PR (whichever status is recorded first) until the first date of documented disease progression, will be estimated using the Kaplan Meier method. Patients without documented progression will be censored at last follow up.
- Adverse events by the current version of Common Terminology Criteria for Adverse Events version 5 (CTCAE v5) will be tabulated in order to assess the safety profile and tolerability of ZW25therapy in patients with recurrent/persistent endometrial cancer.

ADA titers are a continuous variable and these will be assessed descriptively for changes over time as part of exploratory aims.

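### The clinical benefit rate counts stable disease of any duration seen by Week 24, so it measures disease control and not benefit sustained to 24 weeks

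*Combined protocol and SAP*

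**What the plan says.** Section 2.0 lists the secondary objective "To determine Clinical Benefit Rate (CBR) by 24 weeks". Section 14.1 makes it operational as the percentage of patients with "complete response (CR) + partial response (PR) + stable disease (SD) ≤24 weeks from the start of treatment", reported with an exact binomial 90% confidence interval. No null value, target or decision rule is attached, and no analysis population is named for it.

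Section 13.1 defines SD at a single time point as "Neither sufficient shrinkage to qualify for PR nor sufficient increase to qualify for PD", with no element of duration. Best overall response "will be derived during statistical analysis from the series of time point responses"; the repeat assessment at least 4 weeks later is required for CR and PR only. Scans are taken "every 8 weeks through Week 24 and then every 12 weeks after 24 weeks", so the first on-study scan is at Week 8.

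Two other places bear on the point. Section 3.6 reports that phase 1 patients "have experienced disease control (n=32/48 [66.7%]; 15 PRs and 17 stable disease". Section 14.1 bases the design on "historical data from studies with ineffective agents in a similar patient population", giving an overall response rate (ORR) below 10% and a 6-month PFS rate below 20%.

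**The concern.** A rate called clinical benefit and tied to 24 weeks invites the reader to see benefit that lasted 24 weeks. The rule as written asks for less: one scan, as early as Week 8, that does not show progression. In a population where ineffective agents leave fewer than 20% of patients progression-free at 6 months, many patients can pass the Week 8 scan and progress soon after.

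The trial would then report two 24-week figures, CBR and the PFS rate at 24 weeks, that could lie far apart for a reason visible only in the definition. CBR would be the more flattering of the two.

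**Working it through.** **The plan's own figures.** The plan states no CBR for an inactive or an active drug, so there is none to reproduce. Its one design calculation, for ORR, does reproduce. With continuation at 2 or more responses in 16 and success at 5 or more in 25, the probability of success is the sum over x = 2 to 16 of P(X₁ = x) × P(X₂ ≥ 5 − x), where X₁ ~ Bin(16, p) and X₂ ~ Bin(9, p). This gives 0.0951 at p = 10% and 0.9030 at p = 30%, within the stated 10% type I error and 90% power.

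**Does any rule set a minimum SD duration?**
- Section 14.1 uses the same 24-week limit for best overall response in the primary endpoint, where it is plainly the end of a window. Section 2.0 likewise says by 24 weeks.
- Section 13.1 gives SD no duration and confines confirmation to CR and PR.
- The schedule in Section 11.0 adds none.

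So SD at Week 8 followed by progression at Week 16 counts.

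**Size for an inactive drug.** Since the first scan is at Week 8, CBR under the written rule is close to the share alive and progression-free at Week 8. Inputs:
- 6-month PFS s: the plan gives below 20%; the values 5–20% are assumed.
- Week T that stands for 6 months: 24 or 26, assumed.
- Curve shape: exponential, assumed, so S(t) = s^(t/T).

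Example: 0.20^(8/24) = 58.5% and 0.20^(8/26) = 60.9%.

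For the sustained rule, take S(24) and add at most 10 points for responders who progress before Week 24. They would still count, and the plan puts ORR for ineffective agents below 10%.

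| 6-month PFS | Any-SD rule, S(8), T = 24 / 26 | S(24), T = 24 / 26 | S(24) plus 10 points |
|---|---|---|---|
| 20% | 58.5% / 60.9% | 20.0% / 22.6% | 30.0% / 32.6% |
| 15% | 53.1% / 55.8% | 15.0% / 17.4% | 25.0% / 27.4% |
| 10% | 46.4% / 49.2% | 10.0% / 11.9% | 20.0% / 21.9% |
| 5% | 36.8% / 39.8% | 5.0% / 6.3% | 15.0% / 16.3% |

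Even with the full 10 points allowed, the two rules differ by about 28 points at the 20% bound (58.5 − 30.0; 60.9 − 32.6) and by 26–27 points at 10% (46.4 − 20.0; 49.2 − 21.9).

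**Who makes up the difference.** At the 20% bound, S(8) − S(16) is 58.5 − 34.2 = 24.3% (T = 24) or 60.9 − 37.1 = 23.8% (T = 26). That is about 6 of 25 patients who pass Week 8 and progress by Week 16.

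**Sensitivity at the 20% bound.**
- Weibull PFS, S(8) = 0.20^((8/T)^k): 47–49% for k = 0.7 and 73–76% for k = 1.5. S(24) moves little because it lies at or next to the anchor; for example 0.20^((24/26)^1.5) = 24.0%.
- Week 8 scan one week early or late: 55–65%.
- Efficacy population, which drops patients with no post-baseline assessment: if 5–15% were dropped, all without benefit, S(8) becomes 0.585/0.95 = 62% up to 0.609/0.85 = 72%.

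**Precision with 25 patients (exact 90% intervals).** 15/25 gives 41.7–76.4%; 12/25 gives 30.5–65.9%; 7/25 gives 13.9–46.2%.

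**The case against.** The definition is prespecified, agrees between Sections 2.0 and 14.1, and uses the same window as the primary endpoint. Nowhere does the plan promise benefit sustained to 24 weeks. Durability has its own objective, the PFS rate at 24 weeks; Section 14.1 names only the Kaplan-Meier median, but the same curve yields that rate. A CBR above the 24-week PFS rate is expected and is not an error. CBR drives no decision. All of this stands, and it limits the weight of the point.

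Three stronger readings are tempting and should not be drawn:
- That an inactive drug would show a CBR near 60%. This treats an upper bound as the expected value and assumes an exponential curve; the plan gives neither a point value nor a shape.
- That the sustained rule would give only 23–24%. This omits early responders who progress before Week 24, whom the proposed definition still counts.
- That CBR as written cannot tell an active drug from an inactive one. The plan gives no target CBR or PFS from which to show this. The phase 1 figure of 32/48 cannot stand in: it mixes tumour types and dose levels, and only one of the 67 treated patients had endometrial cancer.

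Section 3.6 also states no time window or SD duration for disease control. Equating the two quantities rests on their common make-up (response plus SD), not on a matching definition.

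**Conclusion.** The point holds as one of definition and interpretation. As written, a single SD at Week 8 is enough for clinical benefit. Under exponential PFS with a 6-month rate of 10–20%, an inactive drug could show a CBR of roughly 45–60%. The range is 37–61% for 6-month rates of 5–20%, and about 47–76% at the 20% bound under the other hazard shapes tried. With SD required to hold to Week 24, the figure at the 20% bound would be at most about 20–33%, and lower for lower 6-month rates. These are illustrations under stated assumptions, not predictions for this trial.

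The ORR test, the stage 1 decision and the sample size are untouched. Severity is low to moderate: worth correcting before analysis because the label and the 24-week limit suggest more than the rule measures.

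**What to change.** In Section 14.1, define CBR as CR or PR by 24 weeks, or SD maintained without progression through the Week 24 assessment. Report the any-duration SD rate as a separate line labelled disease control, in keeping with the term in Section 3.6. Name the analysis population for both, and say how a patient with no Week 24 scan is counted. That last rule is needed because patients who stop treatment without progression move to scans every 12 weeks (±3 weeks) under Section 11.0. If the any-SD quantity is what is wanted, relabelling it is enough.

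The cost is wording only: the Week 8, 16 and 24 scans are already scheduled and no sample size changes. The downside is a lower reported CBR, and one that partly overlaps the 24-week PFS rate.

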3. Mandatory pre-treatment and post-treatment tumor biopsies will be obtained on all patients to assess *HER2* expression, its association with treatment response and other genetic changes over time. Attempts will be made to collect 3 cores (Flash Frozen) of tumor material at each time point for research purposes under the current study. Biopsies will only be performed if deemed safe and feasible by the investigator. Post-treatment biopsy will only be done upon progression of disease. Tissue testing will be performed in the CMO. To determine mutational status and/or copy number variations of relevant cancer related genes using MSK-IMPACT platform in patients with response to therapy. MSK-IMPACT tests will be done on new biopsy specimens for research purposes in the context of this protocol. Results from these testing will not be reported to patients.
4. To determine the ability of the laboratory parameters to predict clinical benefit:
 - a. All patients will undergo mandatory pre-treatment fresh tumor biopsy (if deemed clinically safe). Post-treatment fresh tumor biopsy will be done upon disease progression.
5. To evaluate the predictive value of changes in circulating tumor DNA variant allele frequency during treatment for response to ZW25. Circulating plasma cell-free DNA will be collected at pre-treatment (any time prior to C1D1), and at End of Treatment. MSK's standard cfDNA workflow will be followed (one streck tube).
 - a. Liquid biopsy through the sequencing of plasma ctDNA has the potential to address multiple biologic questions, including global tumor heterogeneity. Targeted deep sequencing of candidate driver oncogenes facilitates analysis of the clonal structure of the tumor, and prioritization of clinically relevant actionable targets. As blood content theoretically integrates mutational data from all sites of disease, deep analysis of plasma ctDNA may offer a solution to the problem of assessing intratumoral heterogeneity with tumor biopsies, and ultimately could define a systemic genomic approach to guide application of targeted therapies. A novel bioinformatics algorithm called FACETS developed at Memorial Sloan Kettering will be applied to interrogate clonality from targeted sequencing of ctDNA.

Whole genome or whole exome sequencing will not be done in this study unless activity is seen after data review, at which point the protocol may be amended to include additional objectives.

Incidental Inherited Genomic Findings:

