Survival Status ⁿ												● ⁿ

- a. Within 28 days prior to the start of Cycle 1, Day 1
- b. Directed physical examination is acceptable while on study treatment. Full examination is required at screening and the EOT visit.
- c. Within 14 days prior to the start of Cycle 1, Day 1
- d. Vital signs (blood pressure, pulse, respiration rate, and temperature) will be measured as outlined in the full protocol.
- e. Day 1 laboratory assessments may be performed up to 4 days prior to study agent administration. Laboratory results must be reviewed prior to each scheduled administration of ZW25, with the exception of coagulation testing (PT/INR, aPTT). In the event of severe toxicity, laboratory tests must be repeated as necessary until the toxicity resolves or stabilizes.
- f. For WCBP, a urine or serum pregnancy test will be performed at screening, prior to dosing on Day 1 of every cycle (it can be performed up to 14 days prior to Day 1) and at the 30-day Follow-Up visit. Additional testing may be performed in accordance with institutional requirements or local regulation.
- g. Patients will complete tumor assessments every 8 weeks (from C1D1) until Week 24, then every 12 weeks (± 1 week). If a patient discontinues prior to documentation of PD, a tumor assessment is to be performed at the End of Study visit or 30-Day Follow up visit, if not performed within the previous 6 weeks. Patients who have discontinued study treatment for reasons other than PD will be followed per RECIST 1.1 every 12 weeks (±3 weeks) until documentation of PD, starting a subsequent anti-cancer therapy or for up to one year from Cycle 1, Day 1, whichever comes first.
- h. As clinically indicated.
- i. All AEs and SAEs from the time of informed consent should be recorded.
- j. ECOG assessment is not necessary on Cycle 1 Day 1 if screening assessment was performed within 3 days prior
- k. For logistical reasons such as holidays, a +/- 3 day window applies to all study visits.
- l. Mandatory biopsy at screening and EOT (at time of progression of disease) within 14 days of EOT before initiating new treatment regimen.
- m. Research bloods include ADA and cfDNA sample collection. Research bloods can be collected at screening or cycle 1 day 1 before initiating treatment for baseline collections.

ADA will be collected at baseline and pre-dose at cycles 2, 4, 6, 8, 12, 18, 24 Day 1.

- n. Survival status' can be documented with a phone call or any clinic visits.

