All patients will have their tumors molecularly profiled using the MSK-IMPACT platform, to evaluate for genomic alterations defined by MSK-IMPACT. Testing will (looking for presence/absence of genes at baseline and at end of study) be correlated to objective responses outcomes (binary covariates of CR or PR versus not) in an exploratory manner. Chi square or Fishers' exact test will be used to test this association. A subset analysis of patients who respond and then progress and have post progression material for molecular profiling will be performed in order to determine the mechanism(s) underlying acquired resistance. Specifically, we will be looking for presence of genetic alterations (at progression compared to baseline) which based on their understood biological mechanism may explain

acquired resistance. This analysis will be descriptive with the intention of understanding genetic alterations over time (at progression) and the types of mutation alterations among patients who respond and then progress. Patients will be followed up for a minimum of 12 months. Most variables above are binary (presence/absence) or expressed (yes/no) and they will be tested for association with response (yes/no) using Chi square or Fishers' exact test.

Serial pre- and post-treatment blood samples will be collected for cell-free tumor DNA analysis and sequenced using continuous quantitative methods (digital droplet PCR or hybridization capture next-generation sequencing) for the Rb, CD-K, PI3K- pathway alterations identified by pre-treatment and post-treatment tumor testing and descriptively correlated to clinical outcome. Binary covariates (presence/absence) will be tested for association with response (binary: CR or PR vs not) using Chi square of Fishers' exact test. Circulating tumor DNA is a continuous variable and these will be assessed descriptively for changes over time as part of exploratory aims.

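### Tumor alterations at end of study are tested against response, but that tissue is taken only at progression, so any association cannot be read as predictive of response

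*Combined protocol and SAP*

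**What the plan says.** In section 14.1 the molecular profiling results are to be analyzed by "looking for presence/absence of genes at baseline and at end of study) be correlated to objective responses outcomes". The outcome variable and the status of the analysis follow: "binary covariates of CR or PR versus not) in an exploratory manner". The method is explicit: "Chi square or Fishers' exact test will be used to test this association". Later in the section the intention is repeated for the binary variables generally: "Most variables above are binary (presence/absence) or expressed (yes/no) and they will be tested for association with response (yes/no"). The response variable in the same section is "defined as best overall response of CR or PR versus not", within 24 weeks of starting treatment.

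The source of the end-of-study tissue is set elsewhere. Section 10.0 states: "Post-treatment biopsy will only be done upon progression of disease". It adds a second condition: "Biopsies will only be performed if deemed safe and feasible by the investigator". A footnote to the section 11.0 schedule agrees: "Mandatory biopsy at screening and EOT (at time of progression of disease) within 14 days of EOT before initiating new treatment regimen".

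Section 14.1 also contains a separate descriptive analysis, comparing progression with baseline in patients who respond and then progress. Exploratory objective 3 in section 2.0 asks how genomic changes relate to response, with a view to predictive signatures. Exploratory objective 2 concerns mechanisms of response and resistance.

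**The concern.** Baseline tissue precedes the outcome and can be tested against it. Progression tissue differs in three ways.

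- **Order.** Treatment stops at progression, so a patient's response status is settled when the second biopsy is taken. What is found there cannot have predicted the response.
- **Selection.** Patients who have not progressed supply no tissue, and neither do those for whom biopsy is unsafe or not feasible. Section 14.1 gives no rule for them.
- **Exposure.** Responders will usually have been on ZW25 longer before biopsy. Some of this is built in. The first scheduled scan is at week 8, and section 13.1 requires confirmation at least 4 weeks later. On scheduled dates a confirmed responder's progression tissue therefore comes no earlier than week 8 + 4 = 12, while a non-responder can progress at week 8.

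If alterations accumulate or are selected on treatment, they will be commoner in responders' progression tissue even when they have no bearing on response. What is at stake is the reading of an exploratory result. An alteration that marks time on drug could be carried forward as a candidate predictive signature, and nothing in section 14.1 guards against that.

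**Working it through.** The documents give no figure for these tests to reproduce: no test level, alteration prevalence, acquisition rate or progression times. What follows is an illustration, not an estimate.

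**Inputs from the documents.** There are 25 patients and the promising response rate is 30% (section 14.1). Expected responders are 25 × 0.30 = 7.5, rounded to 8 responders and 17 non-responders.

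**Assumed inputs.** Two-sided Fisher's exact test at 0.05; non-responders progress at 3 months and responders at 9 or 12 months; the alteration is absent at baseline and acquired at a constant monthly rate that does not depend on response. Tissue comes either from everyone (8 v 17) or from fewer patients (5 v 12), to allow for non-progressors and infeasible biopsies.

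**Step 1: prevalence at biopsy** = 1 − exp(−rate × months).

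| Rate per month | Responders, 9 months | Responders, 12 months | Non-responders, 3 months |
|---|---|---|---|
| 0.01 | 8.6% | 11.3% | 3.0% |
| 0.05 | 36.2% | 45.1% | 13.9% |
| 0.10 | 59.3% | 69.9% | 25.9% |

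Example: 1 − exp(−0.05 × 12) = 0.451 and 1 − exp(−0.05 × 3) = 0.139. The odds ratio is (0.451/0.549) ÷ (0.139/0.861) = 5.1.

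**Step 2: chance that the test rejects.** For every pair of counts (a positive among responders, c positive among non-responders), multiply the two binomial probabilities, and sum over the pairs where Fisher's p is at most 0.05. This is exact enumeration.

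| Rate per month | 8 v 17 samples (9 to 12 months) | 5 v 12 samples (9 to 12 months) |
|---|---|---|
| 0.01 | 1.6% to 3.4% | 0.4% to 0.9% |
| 0.05 | 16.1% to 28.0% | 8.1% to 15.2% |
| 0.10 | 25.5% to 44.5% | 17.0% to 29.5% |

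For comparison, if prevalence is equal in both groups at 13.9% or at 45.1%, the 8 v 17 test rejects in 1.1% or 3.0% of trials. If responders progress at 6 months, the 0.05 rate gives only 6.5% with 8 v 17.

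**Step 3: a check with variable progression times.** This used 4,000 simulated trials per setting: 25 patients, 30% response, 10% baseline prevalence, mean progression time of 9 or 12 months in responders against 3 or 2 in non-responders, and tissue available up to 12 or 24 months.

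| Acquisition per month | Rejection, progression tissue |
|---|---|
| 0 | 0.6–1.3% |
| 0.02 | 2.9–6.5% |
| 0.05 | 5.0–14.2% |
| 0.10 | 7.4–24.0% |

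Tests on baseline alterations rejected in 0.6–1.1% throughout. With a 12-month cut-off, about 4.7–5.7 of the expected 7.5 responders had progressed and could give tissue, against about 17 of 17.5 non-responders.

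**The case against.** The strongest reply is that the analysis is labeled exploratory and the plan never says that end-of-study alterations will be called predictors. Objective 2 gives the post-treatment biopsy a proper purpose, and describing progression tissue by response group serves it. Section 14.1 also already contains a descriptive progression-versus-baseline comparison. All of this is fair, and it limits the point to a wording change. It does not remove the point. The descriptive comparison covers only responders who progress, while the association test is a separate sentence with a named hypothesis test. Objective 3's reference to genomic changes leaves room for a predictive reading.

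A reader might go further and infer that the planned test produces false gene–response links. The documents do not support that, for two reasons. First, distortion requires acquisition or selection on treatment, or tissue availability related to the alteration; the documents give no rate for any of these, and with no acquisition the rejection rate matches that of baseline testing. Second, in the illustration the prevalence at biopsy really does differ between the groups. The 28% is therefore the power to detect a real difference, not a false-positive rate. The error would lie in calling that difference predictive.

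It is also fair to object that the higher figures assume everyone progressed and was biopsied. The 5 v 12 column and the variable-time check address this, and both give lower figures.

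**Conclusion.** The point holds as a limit on interpretation. The end-of-study half of the planned test uses a selected sample taken after the outcome, and an association found there cannot be read as predictive of response. That conclusion follows from the text alone.

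The numerical size rests on assumed acquisition rates, progression times, sample counts and a 0.05 level. In the fixed-time illustration the chance of a significant result runs from below 1% to about 45%. At low acquisition rates it stays under the nominal 5%, and at zero there is no exposure-time inflation.

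The baseline half of the same sentence is sound. The point concerns tumor tissue only; end-of-treatment cell-free DNA is not restricted to progression. A reader should not infer any effect on the primary response-rate decision or on the secondary endpoints. This is a cheap improvement of low severity.

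**What to change.** Amend section 14.1 so that tumor-tissue tests of association with response use baseline (pre-treatment) alterations only, by Fisher's exact test. Report progression tissue as paired baseline-to-progression changes in patients with both samples, described by response group without a test against response. State how many responders and how many non-responders supplied progression tissue.

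The cost is wording and one set of exploratory p-values. No biopsy, assay or visit changes.
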